5.3.2. Justification for Use of Placebo Investigational Medicinal Product

A placebo-controlled design is appropriate given the purpose and objectives of this clinical study. Inclusion of a placebo-control group is consistent with the IHS guidelines for controlled trials of drugs in CH, first edition ([Lipton et al 1995](#)).

5.4. Treatment after the End of the Study

Patients who successfully complete the final visit of this study may be offered the opportunity to enroll in a long-term safety extension study (Study TV48125-CNS-30058), which includes a treatment period lasting approximately 40 weeks.

Patients who are discontinued early for any reason or who do not enroll in this long-term study for treatment, for any reason, will be offered the option to enter the study for the purpose of evaluating ADAs and safety (adverse events and concomitant medications) at approximately 7.5 months after administration of the last dose of the IMP. These patients will not receive any doses of fremanezumab after completing participation in the current study and should be treated with standard of care as appropriate.

5.5. Restrictions

Patients will be required to comply with the following restrictions:

5.5.1. Activity

Patients must remain at the site, for safety observation, at least 60 minutes after infusion or according to medical judgment.

5.5.2. Blood Donation

Patients may not donate blood while taking the IMP and for 5 half-lives (7.5 months) after the last dose of the IMP.

5.5.3. Pregnancy

Restrictions in regard to pregnancy and required laboratory values (ie, serum and urine β -HCG tests) are provided in the inclusion and exclusion criteria (Section 4.1 and Section 4.2, respectively). Restrictions in regard to contraception methods are reviewed in [Appendix E](#).

5.6. Prior and Concomitant Medication or Therapy

Any prior or concomitant medication, treatment, or procedure a patient has had 3 months before screening visit (visit 1) and up to the end of study, including follow-up, will be recorded on the CRF. Trade name and INN (if available), indication, dose, and start and end dates of the administered medication will be recorded. The sponsor will encode all medication and treatment according to the World Health Organization (WHO) drug dictionary (WHO Drug).

A maximum of 2 concomitant preventive medications for ECH are allowed. Patients must be on a stable dose and regimen for at least 2 weeks prior to screening and throughout the study. A list of permissible preventive medications is provided in [Appendix H](#).

For daily prescribed medications, patients must be on a stable dose and regimen for at least 2 weeks prior to screening and throughout the study.

All concomitant medications taken during the study must be recorded with indication, daily dose, and start and stop dates of administration. All patients will be questioned about concomitant medication at each visit.

5.7. Procedures for Monitoring Patient Compliance

The investigator will be responsible for monitoring patient compliance. A check of compliance with IMP intake will be performed during each visit after the IMP has been administered, and IMP accountability records will be completed. If the investigator or the sponsor determines that the patient is not in compliance with the study protocol, the investigator and the sponsor should determine whether the patient should be withdrawn from the study. Exposure to IMP will be assessed as required.

5.8. Randomization and Blinding

This is a randomized, double-blind, double-dummy, placebo-controlled study. Patients and investigators will remain blinded to IMP assignment during the study. A computer-generated master randomization list will be provided to drug packaging facilities. Packaging vendor(s) will package active drug and placebo into single-visit kits according to Good Manufacturing Practice procedures. Kits will be identical in appearance and prefilled syringes with test IMP or placebo IMP. Adequate kit supply for upcoming study visits will be managed by IRT and kept (refrigerated at 2°C to 8°C) on site.

Patients will be randomly assigned with stratification based on gender, country, and baseline concomitant preventive medication use (yes/no) to the fremanezumab at 900 mg iv loading dose group, the fremanezumab 675-mg sc quarterly group, or the placebo group in a 1:1:1 ratio. The sponsor, investigators, study staff (except for staff involved in bioanalytical analyses and interim analyses [by a third-party, unblinded statistician]), and patients will be blinded to treatment assignment throughout the study.

The IRT will manage initial drug supply, maintenance of adequate IMP supplies on site, and study randomization centrally.

5.9. Maintenance of Randomization and Blinding

5.9.1. Maintenance of Randomization

The randomization code will be generated by the IRT third-party vendor, following specifications from the Biostatistics Department. A Teva statistician will be responsible for reviewing the dummy randomization codes, and the final randomization code will be maintained by the third-party vendor in a secure location.

At the time of analysis (after the end of the study), after receiving an unblinding request from the Teva statistician, the service provider will provide the unblinded IMP assignments according to the processes defined in the relevant Standard Operating Procedure (SOP).

5.9.2. Blinding and Unblinding

Blinded pharmacokinetics data may be assessed during the study. Personnel responsible for bioanalysis (pharmacokinetics and immunogenicity) will be provided with the randomization code to facilitate the analysis. However, the personnel responsible for bioanalysis and pharmacokinetics data analysis will not have access to clinical safety and efficacy data, and will provide concentration data to other personnel in a manner that will not identify individual patients (ie, a dummy patient identifier will be linked to the concentration data of an individual patient).

The planned interim analysis (Section 9.15) will be conducted by a third-party, unblinded statistician. Results from the interim analysis will be reported in a manner that does not unblind any blinded individuals (ie, the sponsor, investigators, blinded study staff, and patients).

For information about personnel who may be aware of IMP assignments, see Section 5.8. These individuals will not be involved in conduct of any study procedures or assessment of any adverse events.

In case of a serious adverse event, pregnancy, or in cases when knowledge of the IMP assignment is needed to make treatment decisions, the investigator may unblind the patient's IMP assignment as deemed necessary, mainly in emergency situations, through specialized access in the IRT system. If possible, the sponsor should be notified of the event before breaking of the code. If this is not possible, the sponsor should be notified immediately afterwards, and the patient's randomization code should not be revealed. In emergency cases, breaking of the randomization code can be performed by the investigational center without prior approval by the sponsor.

In the event that the IRT system is not functioning for emergency unblinding, the next course of action is to contact via phone the IRT on-call customer support helpline for manual emergency unblinding.

When a blind is broken, the patient will be withdrawn from the study, and the event will be recorded on the CRF. The circumstances leading to the breaking of the code should be fully documented in the investigator's study files and in the patient's source documentation. Assignment of IMP should not be recorded in any study documents or source document.

In blinded studies, for an adverse event defined as a suspected unexpected serious adverse reaction (SUSAR) (ie, reasonable possibility; see Section 7.1.4), Global Patient Safety and Pharmacovigilance may independently request that the blind code be broken (on a case-by-case basis) to comply with regulatory requirements. The report will be provided in an unblinded manner for regulatory submission. If this occurs, blinding will be maintained for the investigator and for other personnel involved in the conduct of the study, and analysis and reporting of the data.

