4.3. Withdrawal Criteria and Procedures

Each patient is free to withdraw from the IMP and/or study at any time, without prejudice to their continued care. Patients must be withdrawn from the IMP and/or study if any of the following events occur:

1. Patient withdraws consent or requests discontinuation from the IMP and/or study for any reason.
2. Patient develops an illness that would interfere with his/her continued participation.
3. Patient is noncompliant with the study procedures and assessments or administration of IMPs in the opinion of the investigator.
4. Patient takes prohibited concomitant medications as defined.
5. A female patient has a confirmation of pregnancy during the study from a positive pregnancy test.
6. The sponsor requests withdrawal of the patient.
7. Patient experiences an adverse event or other medical condition which indicates to the investigator that continued participation is not in the best interest of the patient.
8. The investigator and/or sponsor may withdraw an individual patient from the study at any time for any reason (eg, lack of efficacy, protocol deviation as defined in Section 10, noncompliance, or adverse event). In addition, patients with positive eC-SSRS findings or abnormal hepatic laboratory values (eg, ALT, AST, ALP, GGT, bilirubin [total, direct, or indirect], or INR) may meet criteria for discontinuation from the IMP as summarized in [Appendix J](#).

In the event that a patient was incorrectly randomized and has already started taking the study drug, a risk/benefit evaluation should take place between the investigator and sponsor and a strong clinical justification must be provided if the patient is not withdrawn from study drug.

Patients should be treated with standard of care after withdrawal from or termination of the study as appropriate.

Investigators should attempt to obtain information on patients in the case of withdrawal or discontinuation. Results of any evaluations and observations, together with a narrative describing the reason(s) for withdrawal, must be recorded in the source documents. The case report form (CRF) must document the primary reason for withdrawal or discontinuation.

See [Appendix F](#) for information regarding how the study will define and address lost to follow-up patients to help limit the amount and impact of missing data.

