If a patient is withdrawn from the study for multiple reasons that include also adverse events, the termination page of the CRF should indicate that the withdrawal was related to an adverse event.

An exception to this requirement will be the occurrence of an adverse event that in the opinion of the investigator is not severe enough to warrant discontinuation but that requires the use of a prohibited medication, thereby requiring discontinuation of the patient. In such a case, the reason for discontinuation would be “need to take a prohibited medication” and not the adverse event.

Should a patient decide to withdraw after administration of the IMP or should the investigator decide to withdraw the patient, all efforts will be made to complete and report all observations up to the time of withdrawal. A complete final evaluation at the time of the patient’s withdrawal should be made and an explanation given as to why the patient is withdrawing or being withdrawn from the study.

The reason for and date of withdrawal from the study must be recorded on the source documentation and transcribed to the CRF. If a patient withdraws consent, every attempt will be made to determine the reason.

All protocol-specified procedures/assessments should be performed at the early withdrawal visit (see [Appendix B](#)). Patients who withdraw from the study will not be replaced. Patients who discontinue early for any reason will be offered the opportunity to enter in the long-term safety study (Study TV48125-CNS-30058) for the purpose of evaluation of ADAs and safety (adverse events and concomitant medications) approximately 7.5 months after administration of the last dose of IMP in this study. These patients will not receive any doses of fremanezumab after completing participation in the current study and should be treated with standard of care as appropriate.

A patient should only be designated as lost to follow up if the site is unable to establish contact with the patient after 3 documented attempts via 2 different methods (phone, text, e-mail, certified letter, etc). In the case of patients lost to follow-up, attempts to contact the patient must be made and documented in the patient’s medical records and transcribed to the CRF.

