7.1.2. Recording and Reporting of Adverse Events

For recording of adverse events, the study period for this study is defined as the time period from signature of the ICF through the EOT/early withdrawal visit. Adverse events occurring after the EOT/early withdrawal visit for patients who enroll in the long-term safety study (Study TV48125-CNS-30058) will be recorded as part of the long-term safety study database.

All adverse events that occur during the defined study period must be recorded on the source documentation and transcribed to the CRF, regardless of the severity of the event or judged relationship to the IMP. For serious adverse events and protocol-defined adverse events of special interest (see Section 7.1.7), the serious adverse event form must be completed and the serious adverse event or adverse event of special interest must be reported immediately (see Section 7.1.5.3.1). The investigator does not need to actively monitor patients for adverse events once the study has ended. Serious adverse events and adverse events of special interest occurring in a patient after the defined study period should be reported to the sponsor if the investigator becomes aware of them, following the procedures described in Section 7.1.5.3.1.

At each contact with the patient, the investigator or designee must question the patient about adverse events by asking an open-ended question such as, “Have you had any unusual symptoms or medical problems since the last visit? If yes, please describe”. All reported or observed signs and symptoms will be recorded individually, except when considered manifestations of a medical condition or disease state. A precise diagnosis will be recorded whenever possible. When such a diagnosis is made, all related signs, symptoms, and any test findings will be recorded collectively as a single diagnosis on the CRF and, if it is a serious adverse event, on the serious adverse event form.

The clinical course of each adverse event will be monitored at suitable intervals until resolved, stabilized, or returned to baseline; or until the patient is referred for continued care to a health care professional; or until a determination of a cause unrelated to the IMP or study procedure is made.

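### Section 5.9.2 ends study participation, not only treatment, for any patient whose blind is broken at site level, so a safety event can selectively end data collection

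*Protocol*

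**What the plan says.** Protocol Section 5.9.2 gives the grounds for a break by the investigator: "In case of a serious adverse event, pregnancy, or in cases when knowledge of the IMP assignment is needed to make treatment decisions". It then limits them: "the investigator may unblind the patient's IMP assignment as deemed necessary, mainly in emergency situations". The consequence is fixed and has no stated exception: "When a blind is broken, the patient will be withdrawn from the study, and the event will be recorded on the CRF". The following paragraph covers a code break requested by the sponsor's pharmacovigilance group for a SUSAR: "If this occurs, blinding will be maintained for the investigator and for other personnel involved in the conduct of the study".

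Section 4.3 treats treatment and participation as separable: "Patients must be withdrawn from the IMP and/or study if any of the following events occur". Its list does not name unblinding. For those who leave, "All protocol-specified procedures/assessments should be performed at the early withdrawal visit", and "Patients who discontinue early for any reason will be offered the opportunity to enter in the long-term safety study", where ADAs and safety are evaluated about 7.5 months after the last dose.

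For adverse events, Section 7.1.2 says that "the study period for this study is defined as the time period from signature of the ICF through the EOT/early withdrawal visit". Section 7.1.5 sets the same end for serious events and asks for later ones only if the investigator becomes aware of them. Section 6.1 ends diary entry at the same visit. SAP Section 3.3 requires at least 10 diary days in the first 4 weeks for the full analysis set (FAS). SAP Section 4.5 places early withdrawal data under Last Assessment only, not in the by-visit summaries.

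**The concern.** Once a patient and site know the allocation, diary reports and investigator judgements can be affected. That is a reason to mark the later data. It is not a reason to stop collecting laboratory, ADA, ECG and adverse event data. Section 5.9.2 does not use the distinction that Section 4.3 makes between the IMP and the study.

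The route into the rule is what makes it matter. A serious adverse event is a ground in its own right. Section 7.3 sends overdose cases that need identification of the IMP to the same procedure, and Appendix R allows unblinding for a product quality problem. Observation can therefore end because of a safety outcome. If such events differ between arms, so does the loss. There is no Data Monitoring Committee (Section 5.9.3), so the randomized safety comparison rests largely on the by-arm summaries from which the later data would be missing.

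**Working it through.** The plan gives no figure for serious events or unblinding, so the check is mainly textual, followed by bounds under stated assumptions.

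**1. What stops and what continues after a site-level break**

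- Stops: remaining scheduled visits; diary entry (Protocol 6.1); routine adverse event recording (7.1.2, 7.1.5).
- Done once: the early withdrawal visit, with laboratory tests, ECG, vital signs, examination, PK, ADA and adverse event inquiry (Protocol Appendix B).
- Continues: follow-up of the reported event until it resolves, stabilizes or returns to baseline, or another stated endpoint is met (7.1.2); later serious events if the investigator learns of them (7.1.5).
- Optional: the long-term study (4.3).

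A break before week 4 therefore replaces the week 4, 8 and 12 visits with one early withdrawal visit.

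**2. Diary days lost**

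With a break on day d and diary entry ending then, the loss is 84 − d treatment-period days and max(0, 28 − d) days of the primary window.

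- d = 7: 77 and 21 days lost. At most 7 days are recorded, fewer than 10, so the patient leaves the FAS.
- d = 14: 70 and 14 days lost. The patient stays in the FAS if at least 10 days were recorded, with the available days prorated (SAP 6.1.4.1).
- d = 28: 56 and 0 days lost. The primary window is complete.

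Protocol 9.3.1 counts early terminators as non-responders in responder analyses.

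**3. Number of patients (assumption only)**

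Patients withdrawn = 300 × serious event rate × share unblinded.

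- Lowest: 300 × 0.01 × 0.05 = 0.15
- Middle: 300 × 0.02 × 0.25 = 1.5
- Highest: 300 × 0.05 × 1.00 = 15

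Neither rate is in the documents.

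**4. Power**

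Inputs from Protocol 9.1: difference 1, SD 2, 86 evaluable per group, two-sided alpha 0.05, 14% discontinuation.

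- The plan's figure: Φ(1 / (2 × √(2/86)) − 1.96) = Φ(1.319) = 0.906 (0.903 by noncentral t). It reproduces. So does 258 / 0.86 = 300.
- If all 15 patients were lost in addition to the 14%: (258 − 15) / 3 = 81 per group, and Φ(1 / (2 × √(2/81)) − 1.96) = Φ(1.222) = 0.889.

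**5. Exposure after the last visit**

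Protocol 1.2.2.1 gives a mean half-life of 32.2 to 36.2 days after single sc doses in healthy subjects. On simple first-order decay, the fraction left at 28 days is 2^(−28/32.2) = 0.547 to 2^(−28/36.2) = 0.585. In an actively treated patient, exposure would outlast scheduled observation. This does not apply to placebo patients.

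**The case against.** The strongest reply is that the rule is narrow and the loss partial. Most of that stands.

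- A reader might infer that patients with serious adverse events as a group lose their follow-up. The documents do not say so. Unblinding is permitted, as necessary and mainly in emergencies, so only patients whose code is actually broken are affected.
- A reader might infer that observation ceases altogether. It does not. The early withdrawal visit is complete, and its data enter Last Assessment and the potentially clinically significant summaries (SAP 4.1, 4.5, 8.8). The event itself is followed up, and the extension must be offered. None of these replaces the remaining scheduled visits or captures new non-serious events between them.
- A reader might infer that a patient whose code is broken only by the sponsor for a SUSAR must also be withdrawn, which would alert the site. That reading is strained. The withdrawal sentence closes the text on investigator breaks and refers to site files, while the SUSAR paragraph and Section 7.1.5.3.1 keep study personnel blinded. A clarifying clause is enough.
- The 10-day FAS rule applies to every early leaver, not only to these patients. The first sensitivity analysis in SAP 6.2.3, apparently the multiple imputation, is stated to use the ITT set and so appears to keep them. Its text is largely redacted.
- Section 4.3 allows withdrawal at the sponsor's request or for any reason, so its silence on unblinding is not a strict contradiction. Some of these patients would leave anyway: Section 7.4.1.1 withdraws pregnant patients, and Appendix J sends patients who stop the IMP under its liver rules to the early withdrawal visit. The counts above are therefore not all attributable to 5.9.2.
- Removing unblinded patients is a recognizable choice when the endpoint is a patient diary. It protects the diary data, but it does not justify stopping scheduled laboratory and ADA sampling.

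**Conclusion.** The concern holds for patients whose blind is broken at site level. Section 5.9.2 requires them to leave the whole study, while Section 4.3 keeps treatment and participation apart. After the early withdrawal visit, scheduled visits, diary entry and routine adverse event recording stop. Those with fewer than 10 diary days also leave the FAS, although the ITT-based sensitivity analysis appears to retain them.

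The number affected is likely small. The range of 0.15 to 15 of 300 rests wholly on assumed rates (1% to 5% with a serious event, 5% to 100% of those unblinded). Power is not at stake: even the upper end leaves 0.889. The reason to act is that the loss can be triggered by a safety event and falls on patients whose later safety data are informative.

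**What to change.** Reconcile Section 5.9.2 with Section 4.3 so that a broken blind does not by itself end data collection:

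- Scheduled safety assessments, adverse event recording and diary entry continue unless consent is withdrawn.
- The break is recorded. Diary data and investigator judgements of adverse event severity and causality made after a site-level break are flagged.
- The SAP adds a sensitivity analysis for the flagged diary data.
- One clause in 5.9.2 confirms that a sponsor-only SUSAR code break does not change participation.

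Whether the IMP continues after a break is for the sponsor to state and is not proposed here.

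The cost is one amended paragraph, a flag in the analysis data and one added sensitivity analysis. The downside is that a few diary days and adverse event judgements are made with the allocation known. The flag makes these visible, and the sensitivity analysis covers the diary part.
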